The protocol, informed consent form(s), recruitment materials, and all participant materials will be submitted to the Central Institutional Review Board (cIRB) at the University of Iowa for review and approval. Approval of both the protocol and the consent form must be obtained before any participant is enrolled. Any amendment to the protocol will require review and approval by the cIRB before the changes are implemented to the study. In addition, all changes to the consent form will be cIRB-approved; a determination will be made regarding whether a new consent needs to be obtained from participants who provided consent, using a previously approved consent form.

LIST OF ACRONYMS, ABBREVIATIONS, AND DEFINITIONS OF TERMS

AE	Adverse Event
BPI	Brief Pain Inventory
CDE	Common Data Elements
CFR	Code of Federal Regulations
cIRB	Central Institutional Review Board
CRF	Case report form
CS	Clinically Significant
DCC	Data Coordination Center
DM	Data Management
DSMB	Data Safety Monitoring Board
eCRF	Electronic Case Report Form
EDC	Electronic data capture
EHR	Electronic Health Record
FDA	Food and Drug Administration
FIQR	Fibromyalgia Impact Questionnaire Revised
FM	Fibromyalgia
FM-TIPS	Fibromyalgia TENS in Physical Therapy Study
GAD7	Generalized Anxiety Disorder 7
GCP	Good Clinical Practice
HIPAA	Health Insurance Portability and Accountability Act
ICH	International Conference on Harmonization
IMM	Independent Medical Monitor
MAF	Multidimensional Assessment of Fatigue
MedDRA	Medical Dictionary for Regulatory Activities
NIAMS	National Institute of Arthritis and Musculoskeletal and Skin Diseases
NRS	Numerical Rating Scale
PCS	Pain Catastrophizing Scale
PEG	Pain, Enjoyment, General Activity Scale
PGIC	Patient Global Impression of Change
PHQ-8	Personal Health Questionnaire Depression Scale
PI	Principal Investigator
PROMIS	Patient-Reported Outcomes Measurement Information System
PSFS	Patient Specific Functional Scale
PT	Physical Therapy
RAPA	Rapid Assessment of Physical Activity
SAE	Serious adverse event
SOA	Schedule of Activities
TAPS	Tobacco, Alcohol, Prescription medication, and other Substance use
TENS	Transcutaneous Electrical Nerve Stimulation
SAS	Sit and Stand

SYNOPSIS

Study Title

Fibromyalgia TENS in Physical Therapy Study (FM-TIPS)

Objectives

Primary Objective: Determine if addition of Transcutaneous Electrical Nerve Stimulation (TENS) to routine physical therapy improves movement-evoked pain in patients with fibromyalgia (FM).

Secondary Objectives:

- Determine if addition of TENS to routine physical therapy improves disease activity and symptoms, increases adherence to physical therapy, increases the likelihood of meeting patient specific functional goals, and reduces medication use.
- Examine the feasibility of implementing TENS into routine PT care for FM using semi-structured exit interviews of patients and PTs.

Design and Outcomes

This study is a pragmatic clinical trial in outpatient PT practices utilizing cluster randomization by facility, and facility size. Sites will be randomized to enroll all eligible and consented participants with FM to TENS with PT, or PT only (no TENS). We are identifying 25-35 clinics across 6 healthcare systems in both rural and urban settings. We will enroll 450 patients that self-report a clinician diagnosis of FM. At each site, TENS (or no TENS) will be applied during each PT visit along with individualized PT treatment specified by the physical therapist. Participants randomized to TENS intervention sites will receive TENS units and electrodes at baseline to be applied to the cervical and lumbar regions. They will take the units home and bring the units back to their PT clinic visits with instructions for use at home while active and during their exercises. The physical therapist at each clinic will complete routine documentation of treatment. Variables including adherence to treatment will be extracted from each site's EHR. Additional patient- reported assessments will be obtained from the participants at home the day of their second PT visit and at 30, 60 (primary outcome), 90, and 180 days following enrollment.

Participants will be identified after they are referred for PT for treatment of FM or chronic pain (pain lasting more than three months). At their first (intake) physical therapy visit, they will be provided information about the study that can be accessed on paper or on-line. They will perform an electronic screening form on the first visit if interested in participating. Participants will provide eConsent after eligibility is confirmed at the initial PT visit. At the second PT visit after eConsent is signed, participants will be provided a link to access their survey queue within REDCap™ for data capture and accessing the case report forms. Participants enrolled at a TENS site will then be instructed in use of TENS and the TENS unit with electrodes will be provided. Those participants enrolled at a no TENS site will skip the instruction in use of TENS and TENS units will not be provided until after day 60 assessments are completed at which time they will be instructed in use of TENS by the study team remotely. All participants will be instructed to capture baseline assessments at home (called Research Homework) before their next PT visit. Pain and fatigue will be rated before and following their first TENS treatment (or no TENS) at home (day 1). At 30, 60, 90, and 180 days following enrollment, participants will complete all assessments at home, including pain ratings at rest and with movement along with questionnaires (see below for a list of questionnaires).

Interventions and Duration

For the TENS group, participants will be given TENS devices and electrodes following enrollment during their second PT visit. TENS will be applied to the upper and lower back with butterfly electrodes using the following parameters: mixed frequency (2-125Hz), strong but comfortable intensity, variable pulse duration from 100-250 microseconds. TENS will be applied at home when the patient is active and doing exercises for 2 hours per day and should be brought back to PT visits and used during PT treatment.

For the no TENS group, participants will be given TENS units after the primary endpoint is collected at 60 days. After completion of research homework for Day 60, TENS units will be mailed to the participants. The same instructions for use will be given to the participants as were given to the participants in the TENS group. TENS instructions will be done virtually with a study team member.

Sample Size and Population

Approximately 450 participants will be enrolled at 25-35 practice sites: half of the clinics will be randomized to TENS and the other half of the clinics will be randomized to no TENS.

Inclusion Criteria:

1. Age 18 or above
2. Clinician diagnosis of FM
3. Referred for land-based PT
4. Referred for treatment for FM or chronic pain (pain lasting more than 3 months)
5. Able to provide informed consent
6. Fluent in reading English
7. Willing to use TENS

Exclusion Criteria:

1. Contraindications to TENS use (See Appendix 1 for Precautions and Contraindication references):
 - a. Pacemaker, defibrillator, implanted neurostimulator or implanted device
 - b. Epilepsy
 - c. Currently pregnant or plan to become pregnant in the next 6 months
 - d. Allergic reaction to patches with gel
 - e. Current treatment for cancer
2. Currently enrolled in another pain control study.
3. Use of TENS within the last 30 days.
4. Clinically unstable medical or psychiatric issues

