6.2.3 PT Treatment Visits (In-clinic)

- Apply TENS during exercise treatment (TENS sites and NO TENS sites after day 65 if have in-clinic visit)

6.2.4 30 Day Research Homework (Home +/- 5 days)

- REDCap™ sends participant reminder email to complete Day 30 Research Homework
- Log into REDCap™ (or alternative method) to complete the following assessments
 - Adverse Events
 - Pre-treatment resting NRS for pain and fatigue
 - Pre-treatment Sit and Stand with NRS for pain and fatigue
- Apply TENS (or not)
 - PSFS
 - FIQR
 - BPI
 - PROMIS Physical Function
 - PROMIS-Sleep + Sleep duration
 - PCS
 - PHQ-8
 - GAD-7
 - PGIC
- Post-treatment resting NRS for pain and fatigue
- Post-treatment Sit and Stand test NRS for pain and fatigue
- REDCap™ sends email to study staff that Day 30 Research Homework is complete.

6.2.5 60 Day Research Homework (Home - 5/+10 days)

- REDCap™ sends participant reminder email to complete Day 60 Research Homework
- Log into REDCap™ to complete assessments:
 - Adverse Events
 - Pre-treatment resting NRS for pain and fatigue
 - Pre-treatment Sit and Stand Test with NRS for pain and fatigue
- Apply TENS (or not)
 - PSFS
 - FIQR
 - MAF
 - BPI

- PROMIS Physical Function
- PROMIS-Sleep + Sleep duration
- PCS
- PHQ-8
- GAD-7
- PGIC
- RAPA
- TAPS1
- Post-treatment resting NRS for pain and fatigue
- Post-treatment Sit and Stand Test with NRS for pain and fatigue
- REDCap™ sends email to study staff that Day 60 Research Homework is complete.

6.2.5.1 No TENS Group 65 Day Telehealth Visit by Study Team (Home -5/+15 days)

- Participants in no TENS clinics will be sent a TENS unit and electrodes with written instructions and links to video instructions for use through end of study.
- Study Team provides Telehealth instruction for TENS use, TENS app, and baseline Research Homework with TENS
- Participant completes Baseline Research Homework:
 - Log into REDCap™
 - Pre-treatment resting NRS for pain and fatigue
 - Pre-treatment Sit and Stand with NRS for pain and fatigue
- TENS applied for 1st full treatment X 30 minutes
 - Post-treatment resting NRS for pain and fatigue
 - Post-treatment Sit and Stand with NRS for pain and fatigue
- REDCap™ email sent to study staff when TENS instruction visit complete

6.2.6 90 Day Research Homework (Home +/- 5 days)

- REDCap™ sends participant reminder email to complete Day 90 Research Homework
- Log into REDCap™ to complete assessments:
 - Adverse Events
 - Pre-treatment resting NRS for pain and fatigue

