7 MANAGEMENT OF ADVERSE EXPERIENCES

7.1 Adverse Event Reporting

An adverse event in this study will be defined as an unfavorable and unintended sign or symptom temporally associated with the use of the TENS unit, falls while performing the Sit and stand Test during Research Homework, or another unfavorable sign or symptom limited to problems associated with specific study activities, fibromyalgia symptoms, or hospitalizations/ED visits (see Question 2 below). Pain associated with physical therapy treatment may worsen during the study but will not be classified as an AE.

Adverse events will be queried and recorded on the Participant Experience CRF at each data collection (days 30, 60, 90, and 180) by asking participants the following questions:

"STUDY RELATED

Have you experienced any of the following problems since your last report? (check all that apply)

- Fell during sit and stand test
- Fell or injured yourself during physical therapy exercise at home
- None of the above

Have you had any of the following changes to your health since your last report?

- A pacemaker, implanted neurostimulator or any other implanted device
- A new diagnosis of epilepsy
- A new diagnosis of cancer
- Have become pregnant
- None of the above

Did you experience any of the following since your last report?

Hospitalization? Yes No

i. If yes, please explain: _____

ii. Was the hospitalization related to your TENS use? Yes No

Emergency room visit? Yes No

i. If yes, please explain: _____

ii. Was the emergency room visit related to your TENS use?

TENS RELATED

Have you experienced any problems using the TENS units or electrodes since your last report? Yes No

If yes, what type of problem did you experience? (check all that apply)

- Anxiety with TENS
- Itchiness with TENS
- Nausea with TENS
- Pain with TENS
- Skin irritation with electrodes
- Other TENS related problems

Please list other problems: _____

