7.2 Assessment and Recording of Adverse Events

The study team may contact the participant when an adverse event has been reported to collect further information on the AE, if needed. The team will determine if the adverse event is serious, unanticipated, related to TENS treatment, and if any action needs to be taken, for example, discontinue TENS use, or if further reporting to regulatory authorities is necessary.

Pregnancy:

Pregnancy itself is not regarded as an AE. However, TENS is not recommended for use during pregnancy and the participant will be withdrawn from treatment and the outcome of all pregnancies that occur during paternal or maternal exposure to study device (spontaneous miscarriage, elective termination, normal birth or congenital abnormality) must be followed up and documented even after the participant has been withdrawn from treatment.

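### Controls start TENS around Day 65 without being asked the contraindication items again, and the Day 90 and Day 180 TENS step has no exception for someone who has just reported one

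*Protocol*

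**What the plan says.** **Mailing.** Protocol Synopsis, Interventions and Duration: "After completion of research homework for Day 60, TENS units will be mailed to the participants". No other condition is stated there, and section 6.2.5.1 repeats the dispatch without one. At the end of the Day 60 homework (6.2.5), REDCap "sends email to study staff that Day 60 Research Homework is complete".

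**First use.** Section 6.2.5.1 is headed "No TENS Group 65 Day Telehealth Visit by Study Team (Home -5/+15 days"). Its steps are dispatch of the unit, remote instruction by the study team, pain and fatigue ratings at rest and with the Sit and Stand Test, then "TENS applied for 1st full treatment X 30 minutes".

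**When contraindications are asked about.** Section 7.1: "Adverse events will be queried and recorded on the Participant Experience CRF at each data collection (days 30, 60, 90, and 180"). The form asks "Have you had any of the following changes to your health since your last report" and lists an implanted device, epilepsy, cancer and pregnancy. In the schedule of activities (6.1), the Adverse Events row is blank at Day 65.

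**What staff must do.** Section 6.2.8 takes a participant who develops a contraindication off treatment but keeps them in the study. Section 7.2 says "The study team may contact the participant when an adverse event has been reported to collect further information on the AE, if needed", and then obliges the team to decide whether action is needed, giving discontinuation of TENS as an example. It adds "Pregnancy itself is not regarded as an AE", but a pregnant participant is still withdrawn from treatment. SAP 10.1 counts health changes that affect the ability to use TENS as adverse events, and SAP 10.2 repeats the duty to decide on action.

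**Later homework.** Sections 6.2.6 and 6.2.7 put the Adverse Events form first, then the ratings, then 30 minutes of TENS. The Day 180 list and schedule footnote 3 say that this step is for all participants. The completion email to staff comes last.

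**The concern.** The duty to take a contraindicated participant off TENS works only once someone knows of the contraindication. For controls, the moment that matters is first application, around Day 65. The last scheduled questions come before the unit is mailed, no deadline is set for reading the answers, and the questions are not repeated at the session where TENS starts. A control who reports a change at Day 60, or develops one soon after, could therefore have a first session before the stopping rule takes effect.

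At Days 90 and 180 the participant reports the change and then, in the same sitting at home, meets an instruction to apply TENS before staff are told that the homework is done.

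What is at stake is the safety of a small number of people. Implants, epilepsy and pregnancy are exclusion criteria in Protocol 4.2. For cancer the match is looser: the exclusion is current treatment, while the follow-up item asks about a new diagnosis.

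**Working it through.** This is a check of text and visit windows. No sample size or power figure is involved.

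**1. Inputs.**
- Day 60 homework, −5/+10 days (Protocol 6.2.5): days 55 to 70.
- Day 65 visit, −5/+15 days (Protocol 6.2.5.1): days 60 to 80. SAP Table 5.1 has ±5: days 60 to 70.
- Day 90 homework, ±5 days (Protocol 6.2.6): days 85 to 95.

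**2. Last health answers to first TENS use.**
- Nominal: 65 − 60 = 5 days.
- Longest, Protocol windows: 80 − 55 = 25 days.
- Longest, SAP window: 70 − 55 = 15 days.

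**3. First use to the next scheduled query (Day 90).**
- Nominal: 90 − 65 = 25 days.
- Shortest: 85 − 80 = 5 days. Longest: 95 − 60 = 35 days.
- At up to 2 hours per day, 25 days is up to 50 hours of TENS (range 10 to 70).

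**4. The same interval elsewhere in the trial, for comparison.**
- TENS arm, Day 1 to Day 30: 29 days.
- Both arms, Day 90 to Day 180: 90 days, or up to 180 hours.

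So the interval in step 3 is ordinary for this trial. It reflects the general query schedule and is not a special hazard of the control arm.

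**5. Duties and their timing.**

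| Text | What it requires | Timed before mailing or first use? |
|---|---|---|
| Protocol 6.2.5, completion email | Staff learn that the homework is done | No; it carries no review step |
| Protocol 6.2.8 | Stop TENS if a contraindication develops | No |
| Protocol 7.2 and SAP 10.2 | Team decides whether a reported event needs action | No |
| SAP 10.1 | Health changes that affect TENS use count as events | Not applicable (a definition) |
| Protocol 6.2.5.1 | Staff-led instruction before the first session | Held before use, but lists no health questions |

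**6. Order of steps at Days 90 and 180.** Health items, ratings, TENS for 30 minutes, questionnaires, post-treatment ratings, email to staff. The information needed to skip TENS is already in hand when the TENS step is reached, but no step uses it.

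**7. How many people.** Day 60 completers: 450 × 0.76 = 342. With equal arms, 342 / 2 = 171 controls reach the mailing step. The documents give no rate of new contraindications. Purely as an assumption for scale, 0.5% to 2% gives 171 × 0.005 = 0.9 to 171 × 0.02 = 3.4, or about 1 to 3 people.

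**The case against.** The strongest reply is that the duty to act already exists. Protocol 7.2 and SAP 10.2 oblige the team to decide on action for reported events, the SAP's event definition covers these health changes, 6.2.8 stops treatment, and pregnancy leads to withdrawal from TENS. Section 7.1 also sends serious events reported between homework dates to the medical safety monitor. Controls answer the items nominally only 5 days before first use and then speak to a study team member. All of this stands. What remains is missing timing before mailing, and missing repetition at the one contact where it would be easiest.

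A reader might infer more than the documents support:

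- *That units go out with nobody obliged to look at the answers.* The duty to decide on action is mandatory; only its timing is unstated. The synopsis puts mailing after completion of the homework, which leaves room for review.
- *That controls are less protected than the TENS arm.* TENS participants are screened at Visit 1 and given units at Visit 2 with no listed re-screen, and the interval between those visits is not given.
- *That 50 hours of exposure is a cost of mailing to controls.* Longer intervals between queries occur in both arms.
- *That the plan tells contraindicated people to use TENS.* Read with 6.2.8, a participant already known to be contraindicated is off treatment, and footnote 3 may only mean that former controls now use TENS too. This does not help someone who reports the change in that same homework.

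Finally, SAP 10.1 refers to a Safety Management Plan that is not among the documents, and the REDCap screens are not shown. A hold on dispatch or a branch in the form may exist there.

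**Conclusion.** The point holds as a gap in timing and sequence. The contraindication items are not repeated when controls start TENS, no text places review of the Day 60 answers before mailing or first use, and the Day 90 and Day 180 homework asks for TENS whatever was just reported.

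The window before first use is nominally 5 days, and at most 25 (Protocol) or 15 (SAP). Few people are likely to be affected; the figure of about 1 to 3 rests entirely on an assumed rate and on equal arms. The primary comparison is not affected, because controls start TENS only after their Day 60 outcome is collected.

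This is a cheap improvement in participant safety. It is not evidence that the trial instructs staff to treat contraindicated participants or that no safeguard exists. The conclusion covers the Protocol and SAP only.

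**What to change.** 1. **Day 65 (Protocol 6.2.5.1 and the schedule).** Before the first application, the study team member confirms that the Day 60 health answers have been reviewed and asks the four items again. If any is positive, TENS does not start until the team has decided under 7.2.
2. **Days 90 and 180 (6.2.6, 6.2.7 and schedule footnote 3).** Add to the TENS step: *unless TENS has been discontinued or a contraindication is reported*. Set REDCap to branch on the health answers that already come first, so that the participant skips TENS and still completes the assessments.
3. **Optional.** Require review of the Day 60 answers before mailing. If the Safety Management Plan already does so, cite it in 6.2.5.1.

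Cost: a protocol amendment with cIRB approval before use, a few minutes per control in a session that already takes place, simple branching at two visits, and a short delay in starting TENS for the few who report a change.

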1 STUDY OBJECTIVES

1.1 Primary Objective

The primary objective of the study is to determine if addition of TENS to routine PT improves movement-evoked pain in patients with fibromyalgia (FM).

1.2 Secondary Objectives

The secondary objectives of the study are to:

- Determine if addition of TENS to routine physical therapy improves disease activity and symptoms, increases adherence to physical therapy, increases the likelihood of meeting patient specific functional goals, and reduces medication use.
- Examine the feasibility of implementing TENS into routine PT care for FM using semi-structured exit interviews of patients and PTs.

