3 STUDY DESIGN

This study is a cluster-randomized, pragmatic trial conducted with approximately 450 participants across 25-35 physical therapy clinic sites from 6 health systems. We will employ a stratified randomization based on health system and size of the practice site so that half of the sites will provide TENS in addition to PT for each enrolled participant and the other half of the sites will provide routine individualized PT treatment. In the clinics randomized to standard of care, we will have specific instructions for them not to prescribe TENS to their FM patients. We recognize that some patients may be exposed to TENS through other means (relatives, friends) thus participants in the no TENS sites will also be instructed not to use TENS to prevent cross-ins; however, we believe our sample is sufficiently large to account for this potential exposure of TENS in a no TENS group. Furthermore, participants randomized to the no TENS group will receive TENS after the primary outcome data is collected at day 60 which may also prevent cross-ins and provide equipoise. At the completion of the study, we will specifically ask each participant about their TENS use, regardless of the randomization group. Primary analyses will be based on intention-to-treat.

Participants will be followed for a minimum of 60 days up to a maximum of 180 days with data collection from home at 1, 30, 60, 90, and 180 days following enrollment. The primary outcome variable will be assessed at day 60, which would be approximately at the completion of prescribed PT. Data collected from the PT clinics electronic health records (EHR) periodically

will include ICD 10 coding, the types of treatments (CPT codes), start and end dates for the episode of care, number of visits scheduled, and the number of visits attended. All patient reported measures will be obtained at home via computer, tablet, or phone.

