5 STUDY INTERVENTIONS/STUDY MEDICATION/STUDY DEVICE

5.1 Study Intervention, Administration, and Duration

Participants in the TENS group will be given two TENS devices and electrodes on PT Visit 2. TENS will be applied to the upper and lower back with butterfly electrodes using the following parameters: mixed frequency (2-125Hz), strong but comfortable intensity, variable pulse duration from 100-250 microseconds. TENS will be applied during PT exercise treatment at the clinic and will be used at home when the patient is active or while doing exercise/activity for up to 2 hours per day.

The participants enrolled in the TENS group will use the device during the time of their PT (expected to be approximately 6 weeks but variable according to the individualized PT treatment plan), and after they complete PT for a total of 180 days.

Participants enrolled in the no TENS group will receive TENS units and electrodes after they

complete the primary outcome assessments at 60 days following enrollment to use for the next 120 days. All participants will be allowed to keep their TENS units after the study.

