5.4 Prohibited Concomitant Interventions

5.4.1 Prohibited Interventions

Participants enrolled in a clinic randomized to no TENS will be asked to not use TENS therapy during the first 60 days of study participation. After the 60-day collection of the primary endpoint, participants in no TENS clinics will be given TENS units with instructions on how to use the device.

Participants will not be required to change any of their prescribed medications during the study and no specific medications will be prohibited.

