6 CLINICAL EVALUATIONS/STUDY PROCEDURES

6.1 Schedule of Activities

Evaluation	First and Second PT Intake Visit*	Research Homework before PT Visit 3 (Day 1 ¹)	Treatment Visits	30 +/- 5 days Home ¹	60 - 5/+10 days Home ¹	65 - 5/+15 days Home (No TENS Group Only) ⁴	90 +/- 5 days Home ¹	180 +/- 5 days Home ¹
Eligibility Screen- REDCap™	X							
PSFS		X		X	X		X	X
Informed Consent/ eConsent Review	X*							
Resting NRS pain/fatigue ²		X		X	X	X	X	X
Sit and Stand Test with NRS pain and fatigue pre-treatment ³		X		X	X	X	X	X
TENS applied (or not) x 30 minutes		X	X	X	X	X	X ³	X ³
Demographics		X						
2016 FM Criteria		X						
FIQR		X		X	X		X	X
MAF		X			X			X
BPI		X		X	X		X	X
PROMIS-Physical Function		X		X	X		X	X
PROMIS-Sleep		X		X	X		X	X
PCS		X		X	X		X	X
PHQ-8		X		X	X		X	X
GAD-7		X		X	X		X	X
RAPA		X			X			X
PGIC				X	X		X	X
TAPS1		X			X			X

Concomitant Medications		X						X
Sit and Stand Test with NRS pain and fatigue post TENS or no TENS treatment after 30 min of answering questionnaires		X		X	X	X	X ³	X ³
Adverse Events				X	X		X	X
Barriers to TENS								X

* *Informational activities (e.g., video explaining study, description of TENS) will be delivered at home between PT visits. Consent will be obtained electronically before or as the initial activity of the second PT visit. After the second PT visit, participants will complete Research Homework. Day 1 is designated as the day the baseline study data is collected at home. Baseline data collection should be completed within 10 days of the second PT visit.*

¹*Assessment completed on computer or tablet, phone, or paper at home. If the participant does not have access to a computer, the data will be collected over the phone by the study team and directly entered into the database, or on paper/mailed or Faxed.*

²*Resting NSR pain/fatigue and Sit and Stand Test completed pre and post TENS treatment.*

³*All participants apply TENS*

⁴*Day 65 visit is only performed by the No Tens group*

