6.2.12 Concomitant Medications/Treatments

We will collect categories of concomitant medications used for pain, anxiety/depression, and sleep on a dedicated case report form. We will also collect information on substance use with the TAPS1 instrument at enrollment and at the end of the study.

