6.2.14 Questionnaires

The following questionnaires will be self-administered by participants:

- **Resting NRS for pain and fatigue**-11-point scale
- **Sit and Stand Test** – quantifies movement-evoked pain and fatigue.
- **2016 FM Criteria**- diagnostic criteria for fibromyalgia.
- **PSFS (Patient Specific Functional Scale)** – quantifies activity limitation and measures functional outcomes
- **FIQR (Fibromyalgia Impact Questionnaire Revised)**- 21 items used to evaluate function, overall impact, and symptoms in patients with fibromyalgia.
- **MAF (Multidimensional Assessment of Fatigue)**-16 items measuring fatigue according to four dimensions: degree and severity, distress that it causes, timing of fatigue, and impact on various activities of daily living.
- **BPI (Brief Pain Inventory)**- 11 items measuring pain severity and interference with daily activities.
- **PROMIS-Physical function** – assesses information about physical activities.
- **PROMIS-Sleep+Sleep duration**- 8 items + sleep duration assesses sleep quality and quantity
- **PCS (Pain Catastrophizing Scale)**- 13 items measuring pain magnification, rumination, and helplessness.
- **PHQ-8 (Personal Health Questionnaire Depression Scale)**- 8 items measuring depressive disorders.
- **GAD-7 (Generalized Anxiety Disorder)**- 7 items measuring severity of various signs of generalized anxiety disorder.
- **RAPA (Rapid Assessment of Physical Activity)**- 9 items evaluating current level of physical activity.
- **TAPS (Tobacco, Alcohol, Prescription Medication, and other Substance use)**- 4 item screening tool for substance abuse.

- **PGIC (Patient Global Impression of Change)**- one item evaluating all aspects of patients' health and assesses if there has been an improvement or decline in clinical status.

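### The objective that adding TENS reduces medication use has no TENS versus no-TENS comparison: medication is scheduled only at Day 1 and Day 180, after PT-only participants have received TENS, and no medication endpoint is defined

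*Protocol*

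**What the plan says.** Protocol section 1.2 sets as a secondary objective to determine whether adding TENS to routine PT "increases the likelihood of meeting patient specific functional goals, and reduces medication use". Protocol section 9.1 repeats this as a hypothesis, and SAP section 4 makes the comparison explicit: less medication use than in the PT-alone group.

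On measurement:

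- Protocol section 6.2.12 states: "We will collect categories of concomitant medications used for pain, anxiety/depression, and sleep on a dedicated case report form".
- In the Schedule of Activities (protocol section 6.1) the row "Concomitant Medications" is marked at Day 1 and Day 180 only. The homework lists in sections 6.2.2 to 6.2.7 agree: the form appears at Day 1 and Day 180, and not at Days 30, 60, 65 or 90.

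On crossover, protocol section 5.4.1 states: "After the 60-day collection of the primary endpoint, participants in no TENS clinics will be given TENS units". Section 5.1 says these participants receive units after they "complete the primary outcome assessments at 60 days following enrollment to use for the next 120 days". The schedule has all participants applying TENS at Days 90 and 180.

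On analysis, medications are not among the listed secondary outcomes in protocol section 9.2.2 or SAP section 3. The protocol says only that they are collected, and the SAP points to the visit schedule. SAP section 8 applies the section 7 methods to the section 3 list, and the section 7.2 model has change to Day 60 as its outcome.

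**The concern.** The objective asks about TENS against no TENS. That contrast exists only until PT-only participants receive their units, and no medication record is scheduled after baseline in that period. The first scheduled follow-up record comes when both arms have TENS.

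The risk is one of interpretation. A Day 180 comparison estimates immediate against delayed TENS. If it showed no difference, that could mean that TENS does not change medication use, or that the PT-only arm had caught up, and the data could not separate the two. Catch-up is plausible on the sponsor's own evidence. Protocol section 2.2 reports that in the FAST trial the control groups improved to an equivalent degree once they were given active TENS. That finding concerns symptoms rather than medication, so it shows possibility and not size.

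The missing endpoint adds a second problem. With no variable, time point or model fixed in advance, any medication result would rest on choices made after the data are seen.

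**Working it through.** **Could another source supply the comparison?** The documents state no figure for medication, so the first step is to set their provisions side by side.

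| Source | Timing | Can it serve? |
|---|---|---|
| Medication form (protocol 6.1, 6.2.2, 6.2.7) | Day 1, Day 180 | No follow-up record before crossover |
| TAPS1 (protocol 6.1, 6.2.14) | Days 1, 60, 180 | No: described as a "4 item screening tool for substance abuse", not a record of pain, mood or sleep medication |
| EHR extract (protocol 3) | Periodic | No: it names "ICD 10 coding, the types of treatments (CPT codes), start and end dates for the episode of care" and visit counts, with no medication data |
| Cut-off rule (protocol 3.2) | Day 60 or 90 for participants who cannot reach Day 180 by 11 March 2025 | Unclear: it refers to all patient-reported measures, but the Day 60 and Day 90 lists omit the form |

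**TENS exposure at the Day 180 record**

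- Day 180 ± 5 is Day 175 to 185, which is also the approximate exposure in the TENS arm.
- The PT-only start is the Day 65 visit. The protocol window of −5/+15 (section 6.2.5.1) gives Day 60 to 80.
- PT-only exposure: 175 − 80 = 95 days to 185 − 60 = 125 days; nominally 180 − 60 = 120.
- SAP Table 5.1 gives Day 65 ± 5, so a start at Day 60 to 70: 175 − 70 = 105 days to 125 days.
- Share of TENS-arm exposure: 95/175 = 54% to 125/185 = 68%.

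Two illustrations, neither supported by data in the documents, show how wide the uncertainty is. If the effect grew in proportion to days of use, the Day 180 contrast would keep 100 − 68 = 32% to 100 − 54 = 46% of it. If the effect were complete within 95 days of use, it would keep none.

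**Precision of a Day 60 comparison, were one added**

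Inputs from protocol section 9.3: 342 completers (171 per arm), 13 clinics per arm, CV 0.6. Design effect = 1 + [(1 + CV²)m − 1] × ICC, with m = 342/26 = 13.15.

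As a check on the pain endpoint (difference 1.0, SD 2.0), this formula gives 80.5% power at ICC 0.10 against the stated 81%, and 92.6% at ICC 0.05 against the stated figure of more than 90%. At ICC 0.12 it gives 75.7% against the stated 78%, a gap that does not bear on this point.

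For medication, take a category used by 22% in both arms (the chronic opioid figure cited in protocol section 2.1). The ICC range of 0.05 to 0.10 is an assumption borrowed from the pain outcome. Half-width = 1.96 × √(2 × 0.22 × 0.78 / n_eff).

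| Completers with a Day 60 form | ICC | Design effect | n_eff per arm | 95% CI half-width (points) |
|---|---|---|---|---|
| 342 | 0.05 | 1.84 | 92.7 | 11.9 |
| 342 | 0.10 | 2.69 | 63.6 | 14.4 |
| 169 | 0.05 | 1.39 | 60.6 | 14.7 |
| 169 | 0.10 | 1.78 | 47.3 | 16.7 |

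The 169 rows suppose that only participants enrolled after the ICC recalculation contribute: 450 − 228 = 222, and 222 × 0.76 ≈ 169, so m = 169/26 ≈ 6.5.

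**The case against.** The strongest reply has four parts.

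1. **A randomised Day 180 comparison lies within the plan.** SAP section 6.1 covers secondary outcomes over the six-month follow-up, analysed as randomised, and protocol section 9.4 describes a repeated-measures model with similar analyses for secondary outcomes. But medication is not on either list of secondary outcomes, and such an analysis would still compare immediate with delayed TENS.
2. **The schedule may have an exception.** Under the cut-off rule in protocol section 3.2, some late enrollees might complete the form at Day 60, before crossover. This is a fair reading. It would cover a subset of unstated size, protocol section 6.2.9 refers back to visit lists that omit the form, and no analysis of that subset is planned.
3. **The consequence is limited.** Medication supports no confirmatory claim, and PT adherence sits in the same objective without a listed endpoint either. The first part is right and bounds the importance of the point. The adherence gap is one of definition only, since the EHR extract supplies visits scheduled and attended. For medication the data are missing as well.
4. **A Day 60 form would not yield much.** Participants already past Day 60 cannot be recovered, so the half-width may be nearer 15 to 17 points than 12 to 14, and a category form misses reductions within a category. This stands. It strengthens the case for restating the objective if collection is well advanced.

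**Conclusion.** The concern holds. Reduced medication use compared with PT alone is a stated objective and hypothesis, and the plan as written cannot test it: no medication record is scheduled between baseline and crossover, apart from the ambiguous cut-off provision, and no medication endpoint or model is defined.

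By the only scheduled follow-up record, the PT-only arm has had 95 to 125 planned days of TENS (105 to 125 under the SAP window). These are planned days from the visit windows and assume that use starts at the Day 65 visit; actual use may differ. How far this dilutes a true effect is unknown, and the documents give no basis for choosing between the illustrations above. The damage is confined to this objective.

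**What to change.** **If participants have still to reach Day 60**

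- Add the existing concomitant-medication form to the Day 60 Research Homework, to be completed before units are sent to PT-only participants, and amend the schedule.
- In the SAP, define an endpoint that category data can support. For example: use or non-use of each category (pain, anxiety/depression, sleep) at Day 60, adjusted for baseline use, in a logistic mixed model with a clinic random effect, reported as an estimate with 95% CI.
- Label the Day 180 comparison as descriptive, immediate versus delayed TENS.
- State whether participants who stop at Day 60 or Day 90 under the cut-off rule complete the form at their last assessment.
- Reconcile the Day 65 window between the protocol (−5/+15) and SAP Table 5.1 (± 5).

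**If Day 60 can no longer be collected**, which the March 2025 end date may imply, remove the comparative medication claim or restate it as immediate versus delayed TENS in both documents. This needs only a text change.

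The first route costs one extra form at an existing home assessment, plus a schedule and SAP amendment. It leaves participants already past Day 60 without a value, and its limited precision should be stated in the SAP so that a wide interval is not read as evidence of no effect.
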